6.5.3 Clinical Laboratory Determinations

Blood and urine samples for clinical laboratory tests will be collected at the visits outlined in Table 1. Hematology, chemistry, coagulation parameters (INR), and urinalysis will be conducted at these visits. Serology and the urine drug screen will be conducted at screening (Visit 1). The investigator will assess the clinical significance of any values outside the reference ranges provided by the central laboratory. Participants with abnormalities judged to be clinically significant laboratory values that meet exclusionary criteria, or positive results on the urine drug screen at screening (Visit 1), will be excluded from the study.

Women of childbearing potential will be required to have a urine pregnancy test at all visits. A positive pregnancy test at Visit 1 or Visit 2 will exclude the participant from the study.

Investigators may also perform unscheduled clinical laboratory determinations at any time for the purpose of participant safety.

Participants are not required to fast overnight before coming in for their appointments.

The clinical laboratory parameters to be measured are shown in Table 3.

Table 3 Clinical Laboratory Parameters

Category	Parameter
Chemistry	Sodium, potassium, chloride, bicarbonate, glucose, blood urea nitrogen, creatinine, total bilirubin, alkaline phosphatase, aspartate aminotransferase, alanine aminotransferase, lactate dehydrogenase, creatine kinase, total protein, albumin, calcium, phosphorus, uric acid, total cholesterol. The estimated glomerular filtration rate will be calculated by the central laboratory
Hematology	Hemoglobin; hematocrit; red blood cell count; red blood cell indices (mean corpuscular volume, mean corpuscular hemoglobin, mean corpuscular hemoglobin concentration); white blood cell count including differential (neutrophils, lymphocytes, monocytes, eosinophils, and basophils); platelet count
Urinalysis	Urine dipstick for specific gravity, pH, protein, glucose, ketones, bilirubin, and blood; microscopic exam including red blood cells/high-power field, white blood cells/high-power field, and casts/low-power field
Coagulation	International normalized ratio
Serology	At Visit 1 only: anti-hepatitis A IgM antibody, hepatitis B surface antigen, anti-hepatitis C antibody, anti-hepatitis E IgM antibody

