11.2 CLINICAL LABORATORY PARAMETERS

Descriptive statistics for clinical laboratory values (in International System of units [SI]) at baseline, postbaseline, and changes from baseline values at each postbaseline timepoint will be presented by treatment group for the following laboratory parameters:

Hematology: Hemoglobin, hematocrit, red blood cell count, red blood cell indices (mean corpuscular volume, mean corpuscular hemoglobin, mean corpuscular hemoglobin concentration), white blood cell count, white blood cell count differential (neutrophils, lymphocytes, monocytes, eosinophils, and basophils), and platelet count

Chemistry: Sodium, potassium, chloride, bicarbonate, glucose, blood urea nitrogen, creatinine, total bilirubin, alkaline phosphatase, aspartate aminotransferase, alanine aminotransferase, lactate dehydrogenase, creatine kinase, total protein, albumin, calcium, phosphorus, uric acid, total cholesterol, estimated glomerular filtration rate

Urinalysis: Specific gravity, pH

In addition, descriptive statistics for values and changes from the baseline values in conventional units at each assessment time point will be presented for selected clinical laboratory parameters listed in Appendix 20.1. A description of reporting the lab values in conventional units in participant narratives (along with the standard reporting in SI units) is presented at the end of Appendix 0.

Clinical laboratory test values will be considered potentially clinically significant (PCS) if they meet either the lower-limit or higher-limit PCS criteria listed in Table 11.2-1. The number and percentage of participants who have PCS postbaseline clinical laboratory values will be tabulated by treatment group. The percentages will be calculated relative to the number of participants with available non-PCS baseline values and at least 1 postbaseline assessment for the double-blind

treatment period. The numerator will be the total number of participants with available non-PCS baseline values and at least 1 PCS postbaseline value during the study. A supportive tabular display of participants with PCS postbaseline values will be provided, including the participant identification (PID) number, baseline and all postbaseline (including non-PCS) values.

In addition, a tabular display showing all AEs that occurred in participants who had PCS postbaseline clinical laboratory values will be provided.

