Shift tables from baseline to end of double-blind treatment period for clinical laboratory parameters will be presented by treatment group for the following categories: low, normal, and high, which are provided by lab vendor.

Participants who meet the potential Hy's Law criteria from the first dose of study drug to the end of study will be summarized. Supportive tabular displays will also be provided.

Table 11.2-1. Criteria for Potentially Clinically Significant Laboratory Results

Parameter	SI Unit	Lower Limit	Higher Limit
CHEMISTRY			
Albumin	g/L	< 0.8 × LLN	> 1.2 × ULN
Alanine aminotransferase	U/L	—	≥ 3.0 × ULN
Alkaline phosphatase	U/L	—	≥ 3.0 × ULN
Aspartate aminotransferase	U/L	—	≥ 3.0 × ULN
Bicarbonate	mmol/L	< 0.9 × LLN	> 1.1 × ULN
Bilirubin, total	μmol/L	—	≥ 1.5 × ULN
Blood urea nitrogen	mmol/L	—	> 1.5 × ULN
Calcium	mmol/L	< 0.9 × LLN	> 1.1 × ULN
Chloride	mmol/L	< 0.9 × LLN	> 1.1 × ULN
Cholesterol, total	mmol/L	—	> 1.6 × ULN
Creatinine	μmol/L	—	> 1.5 × ULN
Creatine kinase	U/L	—	> 2.0 × ULN
Estimated glomerular filtration rate	mL/min/1.73m ²	<60 mL/min/1.73m ²	—
Glucose, nonfasting	mmol/L	< 0.8 × LLN	> 2.0 × ULN
Lactate dehydrogenase (LDH)	U/L	—	> 3.0 × ULN
Phosphorus	mmol/L	< 0.9 × LLN	> 1.1 × ULN
Potassium	mmol/L	< 0.9 × LLN	> 1.1 × ULN
Protein, total	g/L	< 0.9 × LLN	> 1.1 × ULN
Sodium	mmol/L	< 0.9 × LLN	> 1.1 × ULN
Uric acid	μmol/L	—	> 1.2 × ULN
HEMATOLOGY			
Basophils, absolute cell count	10 ⁹ /L	—	> 2.0 × ULN
Eosinophils, absolute cell count	10 ⁹ /L	—	> 2.0 × ULN
Hematocrit	Ratio	< 0.9 × LLN	> 1.1 × ULN
Hemoglobin	g/L	< 0.9 × LLN	> 1.1 × ULN
Lymphocytes, absolute cell count	10 ⁹ /L	< 0.7 × LLN	> 1.3 × ULN
Monocytes, absolute cell count	10 ⁹ /L	< 0.5 × LLN	> 2.0 × ULN
Neutrophils, absolute cell count	10 ⁹ /L	< 0.7 × LLN	> 1.3 × ULN
Platelet count	10 ⁹ /L	< 0.5 × LLN	> 1.5 × ULN
Red blood cell count	10 ¹² /L	< 0.9 × LLN	> 1.1 × ULN
White blood cell count	10 ⁹ /L	< 0.9 × LLN	> 1.5 × ULN
URINALYSIS			
pH	pH	< 0.9 × LLN	> 1.1 × ULN
Glucose	—	—	At least 1+
Protein	—	—	At least 1+
Specific gravity	—	—	> 1.1 × ULN

LLN = lower limit of normal value; ULN = upper limit of normal value; normal value provided by laboratory.

SI = Le Système International d'Unités (International System of Units).

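### The only PCS limit for urine specific gravity, 1.1 × ULN, lies at 1.100 or above whatever the ULN, so if no urine sample exceeds 1.100 that row of the PCS table cannot flag anyone

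*SAP*

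**What the plan says.** SAP section 11.2 makes a laboratory value PCS "if they meet either the lower-limit or higher-limit PCS criteria listed in Table 11.2-1". For specific gravity, the table row reads "Specific gravity — — > 1.1 × ULN": no unit, no lower limit, and one multiplicative upper limit. The table footnote defines the reference value as "ULN = upper limit of normal value; normal value provided by laboratory", and neither document prints it.

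On counting, section 11.2 states: "The numerator will be the total number of participants with available non-PCS baseline values and at least 1 PCS postbaseline value during the study". SAP section 16.3 adds that every postbaseline assessment, including repeats and unscheduled samples, enters the PCS determination. A supportive display of participants with PCS values and a display of their adverse events follow from the same flag.

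The parameter is in active use. Protocol section 6.5.3, Table 3, measures it as "Urine dipstick for specific gravity, pH, protein, glucose, ketones, bilirubin, and blood", and SAP section 11.2 lists it among the parameters to be summarised numerically: "Urinalysis: Specific gravity, pH". The SAP also plans a low/normal/high shift display: "Shift tables from baseline to end of double-blind treatment period for clinical laboratory parameters will be presented by treatment group".

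**The concern.** A multiple of the ULN is a sensible way to ask for a value clearly beyond normal when the scale starts at zero, as for an enzyme or creatinine. Specific gravity starts at 1.000, and what varies between urine samples is a small excess over that. Multiplying the whole ratio by 1.1 acts mostly on the constant 1.000 and hardly at all on urine concentration.

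What is at stake is the meaning of the printed result. A PCS row showing 0% in placebo and in both atogepant arms looks like a safety comparison that was made and found nothing. If the limit cannot be reached, the row would read the same under any treatment effect on this parameter.

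**Working it through.** **Inputs**

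- Multiplier: 1.1, upper limit only (SAP Table 11.2-1).
- Specific gravity of water: 1.000, by definition of the quantity.
- ULN: not in the documents. Assumed range 1.000 (the floor, pure water) to 1.050, with 1.020 to 1.040 used for illustration.
- Largest urine value: not in the documents. Assumed not to exceed 1.100; values of 1.035 to 1.080 are used below.

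The plan prints no absolute cut-off, so there is no figure of its own to reproduce.

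**Step 1: the cut-off.** Cut-off = 1.1 × ULN.

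| Assumed ULN | Cut-off |
|---|---|
| 1.000 | 1.100 |
| 1.020 | 1.122 |
| 1.025 | 1.1275 |
| 1.030 | 1.133 |
| 1.035 | 1.1385 |
| 1.040 | 1.144 |
| 1.050 | 1.155 |

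The cut-off rises with the ULN, so 1.100 is its minimum. The unknown ULN therefore does not matter.

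**Step 2: where the height of the cut-off comes from.** Excess of the cut-off over water = 1.1 × ULN − 1 = 0.100 + 1.1 × (ULN − 1). At an assumed ULN of 1.030 this is 0.100 + 0.033 = 0.133. Of 133 thousandths, 100 come from multiplying the constant and 33 from multiplying the excess. Against 30 thousandths at the ULN, a sample would need 133 / 30 = about 4.4 times the excess to be flagged.

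**Step 3: can a sample reach it?** At an assumed ULN of 1.030:

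- 1.040 / 1.030 = 1.010
- 1.050 / 1.030 = 1.019
- 1.060 / 1.030 = 1.029
- 1.080 / 1.030 = 1.049

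All are well short of 1.1. Since the lowest possible cut-off is 1.100, none of the assumed values up to 1.080 is flagged at any ULN in the range.

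**Step 4: the reported percentage.** With no PCS value possible, the numerator is 0, so the percentage is 0 / n = 0% in each arm, whatever n is. Counting repeat and unscheduled samples does not help, because none of them can pass the limit either.

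**Step 5: reporting format.** If the laboratory reports 1030 instead of 1.030, the limit is 1.1 × 1030 = 1133 and nothing changes. If it reported only the excess over water, for example 30, the limit would be 33 and reachable. Nothing in the documents suggests that format.

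**The case against.** The best counter-argument is that specific gravity is well covered elsewhere. Section 11.2 gives descriptive statistics at baseline and each postbaseline timepoint, with change from baseline, by arm. The shift tables use the laboratory's own low/normal/high categories. Section 16.3 puts all assessments in the listings. Protocol section 6.5.3 has the investigator judge the significance of any value outside the reference range. A reader might infer from the PCS row that specific gravity is not examined at all; that is wrong, and this objection stands in full. It limits the harm to one row and its contribution to two linked displays.

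A second objection is that the 0% depends on a ceiling for urine that the documents do not give. That is correct, so the ceiling is stated as an assumption. A mistaken entry could also trigger the flag.

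Third, the empty lower-limit cell is not a fault in itself. Creatinine, blood urea nitrogen, uric acid and several other rows are also one-sided. It matters here only because it leaves the upper limit as the whole test.

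Fourth, a reader might extend the point to urinary pH, whose limits are 0.9 × LLN and 1.1 × ULN. The documents do not support that. With assumed ULNs of 7.5 to 8.5 the upper cut-offs are 8.25 to 9.35, and the lowest of these is below 8.5, itself one of the assumed upper limits of normal. The pH limits are not shown to be out of reach, and a logarithmic scale does not stop a fixed cut-off from working as a flag.

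**Conclusion.** The point holds for specific gravity only, and it is minor. The cut-off is at least 1.100 for every ULN of 1.000 or more. On the assumptions that urine does not exceed 1.100 and that results are reported as a ratio to water (or 1000 times it), the criterion cannot flag any participant and the row is 0% by construction in all three arms.

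That 0% should not be read as evidence of no effect on specific gravity; equally, it does not mean that a real shift would go unseen, since the other displays would show it. Specific gravity is not among the adverse events of special interest in protocol section 6.5.2, and no efficacy, power or multiplicity result depends on this row.

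**What to change.** In SAP Table 11.2-1, replace the multiplicative limit for specific gravity with an absolute limit on the scale the dipstick reports, or with the laboratory's high flag. The sponsor should choose the value. The same table already drops multiples of normal where they do not suit: eGFR has an absolute limit of 60 mL/min/1.73 m², and urine glucose and protein are flagged from a dipstick grade of 1+. The SAP change log records that the eGFR limit was revised because the central laboratory supplied no lower normal value.

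Using the high flag would largely repeat the shift-table classification, so an absolute limit adds more. The alternative is to delete the row and rely on the shift table. That table stops at the end of double-blind treatment, whereas PCS values count throughout the study, so high values during follow-up would then appear only in the descriptive statistics and listings.

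The cost is one table cell and a line of programming, with no new data. The downside is a few more flagged values to list, or one row fewer.

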3.3 Adjudication Committee

An Adjudication Charter will be established and will describe the process for the blinded surveillance, monitoring, and adjudication by the Clinical Adjudication Committee of events of post-treatment elevations of ALT and/or AST $\geq 3 \times$ ULN in the atogepant program. The purpose of this committee charter will be to provide a standardized process for the adjudication of data associated with these events in order to determine whether the elevation was related to atogepant.

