4.0 INTRODUCTION

This statistical analysis plan (SAP) provides a more technical and detailed elaboration of the statistical analyses of the efficacy and safety data as outlined and/or specified in the final protocol (version dated 13 December 2018), protocol amendment 1 (version dated 08 April 2019), protocol amendment 2 (version dated 23 September 2019), and protocol amendment 3 (version dated 29 May 2020) of Study 3101-303-002. Specifications of tables, figures, and data listings are contained in a separate document.

The analyses of the study for global submissions in various geographic regions (US, Europe, etc.) are documented in the main body of this SAP. Additional analyses for subjects enrolled at study sites in China, Japan, Korea, and Taiwan that will be used to provide additional support for marketing authorization in the above countries or region are documented in region-specific SAP Addenda.

This is a multicenter, randomized, double-blind, placebo-controlled, parallel-group, Phase 3 study conducted at approximately 110 sites worldwide. Approximately 750 participants will be randomized to 1 of 3 treatment arms (placebo, Atogepant 30 mg twice daily [BID], and Atogepant 60 mg once daily [QD]) in a 1:1:1 ratio.

Participants will be stratified by:

- Randomization will be stratified by use of acute headache medications during the baseline period (acute headache medication overuse Yes or No). Acute headache medication overuse (Yes) will be defined as follows: use of triptans on ≥ 10 days OR use of ergots on ≥ 10 days OR use of simple analgesics (ie, aspirin, nonsteroidal anti-inflammatory drugs [NSAIDs], or acetaminophen) on ≥ 15 days OR use of any combination of triptans, ergots or simple analgesics on ≥ 10 days.

- Approximately 70% of randomized participants will have taken at least 1 prior migraine prevention medication with proven efficacy. Randomization will be stratified based on migraine prevention medication exposure (Current Use, Past Use, or Never Used) with proven efficacy. Participants with current or past use will be further stratified based on the number of medications failed with unique mechanisms of action: “failed 0 medications or failed 1 or more medication(s) with the same mechanism of action” or “failed 2 to 4 medications with different mechanisms of action”. Enrollment of participants with current use of a migraine prevention medication will be capped at ~15%.

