7.0 PARTICIPANT DISPOSITION

The number of participants screened will be summarized overall by study center; the number of participants in the ITT, Safety, mITT, and Off-treatment Hypothetical Estimand Populations will be summarized by treatment group and study center.

The number and percentage of participants in the ITT Population will be summarized by treatment group for the following two categories:

- IWRS randomization stratification: acute headache medication overuse (Yes or No), migraine prevention medication exposure (Current Use, Past Use, or Never Used) and number of medications failed with unique mechanisms of action (“failed 0 medications or failed 1 or more medication(s) with the same mechanism of action” or “failed 2 to 4 medications with different mechanisms of action”). The number and percentage of participants in the ITT Population will also be summarized by treatment group for each randomization stratum of 10 strata (the combination of 2 levels of “acute headache medications during the baseline period” (acute medication overuse Yes/No) and 5 levels of “current and past use of migraine prevention medications and the number of medications failed with unique mechanisms of action” (Current Use and “failed 0 medications or failed 1 or more medication(s) with the same mechanism of action”, Current Use and “failed 2 to 4 medications with different mechanisms of action”, Past Use only and “failed 0 medications or failed 1 or more medication(s) with the same mechanism of action”, Past Use only and “failed 2 to 4 medications with different mechanisms of action”, and Never Used) .
- Derived stratification: raw data from the database will be used to re-derive the “actual” stratification based on algorithms detailed in the SAP Section [16.10](#).

A summary table and list of participants with inconsistent randomization stratum against IWRS will be provided.

Screen-failure participants (ie, participants screened but not randomized) and the associated reasons for failure to randomize will be tabulated overall for all screened participants. The number and percentage of participants who enter the double-blind treatment period, complete the double-blind treatment period and of participants who prematurely discontinue during the double-blind treatment period will be presented for each treatment group and pooled across treatment groups

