11.1 ADVERSE EVENTS

Adverse events will be coded by system organ class and preferred term using the *Medical Dictionary for Regulatory Activities (MedDRA)*, version 21.1.

An AE will be considered as a treatment-emergent adverse event (TEAE) if the AE began or worsened (increased in severity or became serious) on or after the date of the first dose of double-blind study treatment. However, an AE that occurs more than 30 days after the last dose of double-blind study treatment or Visit 8 whichever comes later will not be counted as a TEAE. Per case report form instructions, a new AE record will be created with a new AE onset date for any AE that worsens. Therefore, TEAEs can simply be identified as those AEs with recorded onset date on or after the date of the first dose of double-blind study treatment and within 30 days after the last dose of double-blind study treatment or Visit 8 whichever comes later. TEAEs that started after the date of last dose of study treatment will be considered as newly emergent.

Only AEs captured in study 3101-303-002 will be considered for TEAEs in this study. For participants rolling over into studies 3101-306-002, 3101-311-002 or 3101-312-002 (extension studies) who start the first dose on Visit 1 or beyond, AEs captured in those studies will be summarized in those studies although some AEs might occur within 30 days after the last dose from study 3101-303-002.

Overall summary of AEs will be provided on a per-participant basis for categories of TEAEs, treatment-related TEAEs, serious adverse events (SAEs), deaths, and AEs leading to study intervention discontinuation.

The number and percentage of participants reporting TEAEs in each treatment group will be tabulated by descending percentage in Atogepant 60 mg QD group, by system organ class and preferred term, and further categorized by severity and causal relationship to the study treatment. If more than 1 AE is coded to the same preferred term for the same participant, the participant will be counted only once for that preferred term using the greatest severity and strictest causality for the summarization by severity and causal relationship.

For “current use” of migraine prevention medication participants, the number and percentage of participants reporting TEAEs in each treatment group will be tabulated by system organ class and preferred term.

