The number and percentage of participants meeting each of the following criteria for postbaseline hepatic laboratory abnormalities listed in [Table 11.2-2](#) will be summarized by treatment group. The percentages will be calculated relative to the number of participants with at least 1 available postbaseline assessment. The numerator will be the total number of participants having at least 1 postbaseline value that meets the specific category during the study. A supportive listing will also be provided.

Table 11.2-2. Criteria for Hepatic Laboratory Abnormalities

Laboratory Parameter	Categories
ALT	$\geq 1 \times \text{ULN}$
	$\geq 1.5 \times \text{ULN}$
	$\geq 2 \times \text{ULN}$
	$\geq 3 \times \text{ULN}$
	$\geq 5 \times \text{ULN}$
	$\geq 10 \times \text{ULN}$
	$\geq 20 \times \text{ULN}$
AST	$\geq 1 \times \text{ULN}$
	$\geq 1.5 \times \text{ULN}$
	$\geq 2 \times \text{ULN}$
	$\geq 3 \times \text{ULN}$
	$\geq 5 \times \text{ULN}$
	$\geq 10 \times \text{ULN}$
	$\geq 20 \times \text{ULN}$
ALT or AST	$\geq 1 \times \text{ULN}$
	$\geq 1.5 \times \text{ULN}$
	$\geq 2 \times \text{ULN}$
	$\geq 3 \times \text{ULN}$
	$\geq 5 \times \text{ULN}$
	$\geq 10 \times \text{ULN}$
	$\geq 20 \times \text{ULN}$
Bilirubin Total	$\geq 1 \times \text{ULN}$
	$\geq 1.5 \times \text{ULN}$
	$\geq 2 \times \text{ULN}$
	$\geq 3 \times \text{ULN}$
	$\geq 5 \times \text{ULN}$
	$\geq 10 \times \text{ULN}$
	$\geq 20 \times \text{ULN}$
Alkaline Phosphatase	$\geq 1 \times \text{ULN}$
	$\geq 1.5 \times \text{ULN}$
	$\geq 2 \times \text{ULN}$
	$\geq 3 \times \text{ULN}$
	$\geq 5 \times \text{ULN}$
	$\geq 10 \times \text{ULN}$
	$\geq 20 \times \text{ULN}$
Concurrent Elevations ¹	ALT or AST $\geq 3 \times \text{ULN}$ and Bilirubin Total $\geq 1.5 \times \text{ULN}$
	ALT or AST $\geq 3 \times \text{ULN}$ and Bilirubin Total $\geq 2 \times \text{ULN}$
Potential Hy's Law ¹	ALT or AST $\geq 3 \times \text{ULN}$ and Bilirubin Total $\geq 2 \times \text{ULN}$ and ALP $< 2 \times \text{ULN}$

ALT = alanine aminotransferase; AST = aspartate aminotransferase; TBL = total bilirubin; ALP = alkaline phosphatase; ULN = upper limit of normal (value provided by the laboratory).

¹ Elevations are from the same day

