The number and percentage of participants with an adjudicated case (i.e., $ALT \geq 3 \times ULN$ and/or $AST \geq 3 \times ULN$) will be summarized by treatment group and by relationship of ALT or AST elevation to study medication. The percentages will be calculated relative to the number of participants with at least 1 adjudicated case. The numerator will be the number of participants with at least 1 adjudicated case in the specific category of relationship. If a participant has more than 1 adjudicated case, he or she will be counted in the most relevant category of relationship.

Participants with an adjudicated case (i.e. $ALT \geq 3 \times ULN$ or $AST \geq 3 \times ULN$) will be listed with their ALT and AST assessments, adjudication dates, relationship of ALT or AST elevation to study medication, and confounding factor(s). Additional listings will be provided for participants who meet $ALT \geq 3 \times ULN$ or $AST \geq 3 \times ULN$ and/or potential Hy's law and have one of the following categories: at least 1 abnormal liver biochemistry risk factor, at least 1 liver disease sign and symptom, at least 1 liver diagnostic test performed, consultation with a specialist for liver evaluation, liver lab tests performed, and drug screen performed, respectively.

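### Do the adjudicated ALT/AST percentages, taken as shares of an arm's cases, hide the per-arm risk of drug-related liver enzyme elevation?

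*SAP*

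**What the plan says.** Protocol 3.3 sets up a blinded committee to review post-treatment ALT or AST elevations of at least 3 × ULN, "in order to determine whether the elevation was related to atogepant". SAP 11.2 plans the number and percentage of participants with an adjudicated case, by treatment group and relationship category. The denominator is fixed: "The percentages will be calculated relative to the number of participants with at least 1 adjudicated case". So is the numerator: "The numerator will be the number of participants with at least 1 adjudicated case in the specific category of relationship". A participant with several adjudicated cases is counted in one category only. Participants with a case "will be listed with their ALT and AST assessments, adjudication dates, relationship of ALT or AST elevation to study medication", together with confounding factors.

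The same section plans Table 11.2-2, which has a row for ALT or AST of at least 3 × ULN by treatment group on a different base: "The percentages will be calculated relative to the number of participants with at least 1 available postbaseline assessment". In SAP 11.1, treatment-emergent adverse events are "further categorized by severity and causal relationship to the study treatment". SAP 7.0 reports arm sizes: "the number of participants in the ITT, Safety, mITT, and Off-treatment Hypothetical Estimand Populations will be summarized by treatment group and study center". Table layouts are outside the SAP: "Specifications of tables, figures, and data listings are contained in a separate document".

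**The concern.** Safety is a stated objective, ALT or AST of at least 3 × ULN is an adverse event of special interest (Protocol 6.5.2), and Protocol 1.2 records that an earlier oral drug of this class was dropped after ALT increases. The committee's finding on causality is therefore something a reader will look for. Yet the percentage attached to it takes no account of how many people were exposed. In each arm the categories add to 100%, whether there were 2 cases or 20, and an arm without a case has no percentage at all.

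The neighbouring Table 11.2-2 divides by assessed participants. Someone moving from that table to the adjudicated one could take a share of cases for a risk, see the same figure in two arms, and conclude that related elevations were equally common. No other planned percentage corrects this directly. Table 11.2-2 and the table of potentially clinically significant values have no split by relationship, and the adverse event tables use the investigator's causality (Protocol 9.1.4) and not the committee's.

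**Working it through.** The plan states no figure on this point, so there is none to reproduce. The check has three parts.

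**1. Which planned outputs cover ALT/AST elevation and causality**

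| Planned output | Split by relationship | Denominator |
|---|---|---|
| Adjudicated cases (SAP 11.2) | Yes, committee | Participants with a case |
| Table 11.2-2, ALT or AST ≥ 3 × ULN | No | Participants with a postbaseline assessment |
| Potentially clinically significant ALT, AST (Table 11.2-1) | No | Participants with a baseline value not meeting the criterion and a postbaseline assessment |
| Adverse events by causality (SAP 11.1) | Yes, investigator | Not stated in the SAP for this table; Safety Population analysis |
| Listing of adjudicated cases (SAP 11.2) | Yes, committee | None; one entry per participant |

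No row combines the committee's category with an assessed or exposed denominator. On the text, the observation is correct.

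**2. How far share and incidence can diverge**

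Let *c* be the participants with an adjudicated case in an arm, *r* those whose case is judged related, and *N* the arm size. The planned percentage is *r/c* and the incidence is *r/N*. *N* = 250 is the planned size (Protocol 3.1). The documents give no case rate and no related share, so every *c* and *r* below is an assumption.

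| Related / cases | Planned percentage | Incidence |
|---|---|---|
| 1 of 2 | 1/2 = 50% | 1/250 = 0.4% |
| 3 of 6 | 3/6 = 50% | 3/250 = 1.2% |
| 1 of 1 | 1/1 = 100% | 1/250 = 0.4% |

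Equal shares can go with a threefold difference in incidence, and 1 of 1 against 3 of 6 puts the arms in the opposite order.

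To see how often this might happen, take cases as Binomial(250, *p*) and related cases as Binomial(*c*, *s*), for placebo and one atogepant arm. Set *p* at 1% on placebo and 2% or 3% on atogepant, with *s* (placebo/atogepant) at 25/25, 50/50, 75/75, 25/50 and 20/60 percent. Exact enumeration over these ten settings, restricted to outcomes with more related cases on atogepant, gives:

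- shares rank the arms as the counts do: 39% to 83%
- shares rank them the other way: 6% to 44%
- shares tie: 2% to 14%
- placebo share undefined because it has no case: 8% to 12%

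The restriction itself holds with probability 0.52 to 0.96 across the ten settings.

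**3. What a reader needs to recover the incidence**

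The numerator *r* is printed, because the SAP plans number and percentage by arm and category. *N* is in the disposition summary. The assessed denominator goes with Table 11.2-2. In the example, the planned table would show 1 (50%) and 3 (50%); dividing 1 and 3 by 250 gives 0.4% and 1.2%. An undefined percentage goes with a printed count of zero.

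**The case for a change.** The strongest argument for a change is that it would be nearly free: one sentence and one extra column, using a denominator the SAP already applies to the same enzymes, in an area where the drug class has a history. A percentage laid out by treatment group invites comparison between groups, and part 2 of the check shows that such a comparison can mislead.

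What stands is that the share should not be read as a risk. What does not stand is that the plan is deficient without the extra column.

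In a randomized placebo-controlled trial, the sound between-arm comparison is the incidence of elevation whatever its attributed cause, since it needs no judgement about individual cases. That comparison is planned. The adjudicated table answers a different question, namely how the blinded committee classified the cases it saw, and a share of cases is a natural summary for that.

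The enumeration also carries limited weight. Its case rates have no anchor in the documents, all ten settings assume more cases on atogepant, and only one of the two atogepant arms is modelled. It describes a reader who ignores both the printed counts and the stated denominator. Because the table layouts are in a separate document, one cannot say whether arm sizes already stand beside the counts.

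**Conclusion.** The reading of SAP 11.2 is right, but no change to the plan is needed. The adjudicated percentages are shares of an arm's cases, and no planned percentage gives the per-arm incidence of elevation that the committee judged related. In the worked example this hides 0.4% against 1.2% behind two figures of 50%; the size rests wholly on assumed counts at 250 per arm.

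Nothing is lost. Counts, a case-by-case listing, arm sizes and the incidence of ALT or AST of at least 3 × ULN regardless of cause are all planned, and no hypothesis test, alpha allocation or decision rule touches this percentage. If the SAP is followed as written, the liver safety results and the conclusion drawn from them are the same with or without the extra column. Whoever writes the study report should describe these figures as shares of cases and quote the counts with them, which the plan already allows.

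The conclusion assumes that the denominator is taken within each arm, as the layout by treatment group implies. If cases were pooled over arms, the percentage would still be a share of cases and the same reasoning would apply.
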